### **10.2.2 Evaluable Analysis Set**

The Evaluable Analysis Set (EAS) is a subset of the FAS and includes all participants treated with at least one dose of capmatinib monotherapy, who have measurable disease at baseline, and centrally confirmed MET amplification. This analysis set will be used for the primary efficacy endpoint and the analysis of the secondary efficacy endpoints at the interim and primary analysis.

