### Group 5 (EGFRmut, T790M-, MET GCN $\geq$ 5, 2L, EGFR TKI resistant)

An interim analysis for futility will be performed based on stage 1 of the 2-stage design of Group 5 when 10 participants have completed at least 2 tumor assessments while on treatment with capmatinib monotherapy, had radiological disease progression per RECIST 1.1, or discontinued capmatinib monotherapy treatment prior that time. Recruitment will be on temporary halt while conducting the IA. The IA will be based on the EAS.

The decision to stop for futility at the interim analysis will be based on the predictive probability (PP) that the final observed ORR of capmatinib monotherapy is no worse than the historical control ORR, given the interim observed data (x) and responders among n participants. Based on available data (Soria et al 2015, Mok et al 2017), the ORR in the historical control for this population is expected to be around 35%. Thus, the stop for futility rule is based on

$$PP = \text{Prob}[\text{Final observed ORR of capmatinib monotherapy} \geq 35\% \mid x, n]$$

A minimally informative Beta distribution prior with prior mean equal to 35% will be used, i.e., the prior distribution will be Beta (0.5385, 1) for the futility stopping decision rule calculations at the interim analysis.

The group will be stopped for futility at the interim analysis if the PP <1%, i.e., if 0 response out of the first evaluable 10 participants is observed. For the purpose of the interim analysis a responder is defined as participant having a response of PR or CR per RECIST 1.1.

All evaluable participants at the time of the data cut-off for the interim analysis will be used to obtain the futility boundary using the stopping criteria. The futility boundary will be calculated according to the actual number of evaluable participants (in the EAS) in the interim analysis.

Table 10-3 presents the PP at the final analysis based on different numbers of responders observed at the interim analysis and an observed ORR of not worse than 0.35 for capmatinib monotherapy.

**Table 10-3 Predictive probability (PP) for ORR of capmatinib monotherapy at the final analysis based on various numbers of responders observed at the IA for Group 5**

Responders at IA out of 10 evaluable participants at IA	Predictive probability (PP)
0	0.0000
1	0.0148
2	0.0984
3	0.3207
4	0.6301
5	0.8686
6	0.9720
7	0.9967
8	0.9998
9	1.0000
10	1.0000

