**Table 10-7 Operating characteristics for various assumed true ORR of capmatinib monotherapy**

True ORR	Probability to stop at IA* (%)	Probability of positive conclusion at final analysis (%)	Probability of negative conclusion at final analysis
0.10	34.87	0.00	65.13
0.20	10.74	0.09	89.17
0.25	5.63	0.82	93.55
0.30	2.82	4.00	93.17
0.35	1.35	12.63	86.02

True ORR	Probability to stop at IA* (%)	Probability of positive conclusion at final analysis (%)	Probability of negative conclusion at final analysis
0.40	0.60	28.55	70.85
0.45	0.25	49.75	50.00
0.50	0.10	70.76	29.14
0.55	0.03	86.44	13.53

\*Assuming interim analysis at 10 evaluable participants

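### The Group 5 futility rule is stated in two ways that agree only at 10 participants, and the recalculated version can count dosed but unscanned participants as non-responders

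*Protocol*

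**What the plan says.** Protocol Section 10.9 (Group 5) times the interim for when 10 participants have had two tumor assessments on capmatinib monotherapy, have progressed radiologically, or have discontinued. The analysis set is the EAS. The group stops "if the PP <1%, i.e., if 0 response out of the first evaluable 10 participants is observed".

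The same section then says that "All evaluable participants at the time of the data cut-off for the interim analysis will be used to obtain the futility boundary", and that "The futility boundary will be calculated according to the actual number of evaluable participants (in the EAS) in the interim analysis". On accrual it says only that "Recruitment will be on temporary halt while conducting the IA".

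Section 10.2.2 defines the EAS as the part of the FAS that "includes all participants treated with at least one dose of capmatinib monotherapy, who have measurable disease at baseline, and centrally confirmed MET amplification". It sets no minimum follow-up and asks for no post-baseline assessment.

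Table 10-3 gives the PP for 0 to 10 responders out of 10. Table 10-7 (Section 10.10) gives the probability of stopping at the interim by true ORR, with the footnote "Assuming interim analysis at 10 evaluable participants". The shown text gives no boundary or stop probability for any other n. Section 10.10 also allows extra enrolment so that stage 1 has at least 10 centrally confirmed participants.

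**The concern.** The two statements of the rule give the same answer only if exactly 10 EAS participants exist at the data cut-off. The text lets there be more. A participant still on treatment needs two scans to meet the trigger. Section 7.2.1 starts scans at Cycle 3 and repeats them every 8 weeks, so that is about 16 weeks. Nothing in the shown text stops recruitment during that wait. Anyone dosed in the meantime who has measurable disease and central MET confirmation belongs to the EAS, whether scanned or not.

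The PP formula treats each such person as a completed non-response. The decision on the same 10 mature participants could then turn on how many others happen to have been dosed, and Table 10-7 does not describe the risk of that decision. What is at stake is stopping an active group on immature data. Section 8.5 says that no independent data monitoring committee is formed, and the stop is worded as something that will happen, so the sentence defining the dataset carries the whole decision.

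**Working it through.** **Inputs.** From Section 10.9: stop if PP < 1%; PP is the chance, given the interim data, that the final observed ORR is at least 35%; "the prior distribution will be Beta (0.5385, 1) for the futility stopping decision rule calculations". From Section 10.10: final N = 30. Since 0.35 × 30 = 10.5, the final target is at least 11 responders.

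**Formula.** With x responders among n at the interim, the number of further responders among 30 − n follows a beta-binomial distribution with parameters 0.5385 + x and 1 + n − x. PP(x, n) is the probability that this number is at least 11 − x. The boundary is the largest x with PP < 0.01.

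**Reproducing the plan's figures.** At n = 10 the formula returns Table 10-3 to four decimals for x = 1 to 10 (x = 1: 0.0148; x = 2: 0.0984; x = 3: 0.3207). For x = 0 it gives 0.0006 where the table prints 0.0000, which does not affect the rule. Every stop probability in Table 10-7 equals (1 − p)^10. For example, 0.65^10 = 1.35%, 0.55^10 = 0.25% and 0.50^10 = 0.10%. The column is the fixed 0-of-10 rule, as its footnote indicates.

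**Boundary when n exceeds 10 (N = 30).**

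- n = 11: PP(1, 11) = 0.0077, so one response is now a stop.
- n = 14: PP(1, 14) = 0.0007 and PP(2, 14) = 0.0102, so the boundary is still 1.
- n = 15: PP(2, 15) = 0.0049, so the boundary is 2. It stays at 2 for n = 16, where PP(3, 16) = 0.0201.

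**Stop probability.** Two cases were run. In case A all n counted participants are mature: P(X ≤ boundary) with X ~ Bin(n, p). In case B only the 10 trigger participants are mature and the others are counted with no response: P(X ≤ boundary) with X ~ Bin(10, p).

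| n in EAS | Boundary | A: ORR 45% / 50% | B: ORR 45% / 50% |
|---|---|---|---|
| 10 | 0 | 0.25% / 0.10% | 0.25% / 0.10% |
| 11 | 1 | 1.39% / 0.59% | 2.33% / 1.07% |
| 12 | 1 | 0.83% / 0.32% | 2.33% / 1.07% |
| 14 | 1 | 0.29% / 0.09% | 2.33% / 1.07% |
| 15 | 2 | 1.07% / 0.37% | 9.96% / 5.47% |
| 16 | 2 | 0.66% / 0.21% | 9.96% / 5.47% |

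In case A the risk at ORR 45% stays below 2% for every n up to 21; the highest value is 1.89%, at n = 20. In case B it keeps rising with n: 26.6% / 17.2% at n = 17 to 19, where the boundary is 3, and 50.4% / 37.7% at n = 20, where it is 4. Those rows need 7 to 10 unassessed EAS participants.

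**Same mature data, different decision.** One response in 10 gives PP 0.0148 and the group continues. With one unassessed participant added, PP is 0.0077 and it stops. Two responses in 10 give PP 0.0984 and the group continues. With five unassessed participants added, PP is 0.0049 and it stops.

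**The case against.** Table 10-7 is openly conditioned on 10 evaluable participants and is right for that case. Section 10.9 also ties the zero-response rule to an interim with 10 evaluable participants. Recalculating a pre-specified PP boundary at the actual n is a legitimate design, and Group 3 bases its criterion on actual numbers too. All of this stands. What it leaves open is who counts in n.

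A reader might infer that one extra participant puts an active drug at serious risk. The figures do not support that. At n = 11 the stop risk is at most 2.3% at ORR 45%, and the chance of passing the interim and reaching 14 of 30 responders moves only from 49.75% to 49.63%. More frequent stopping at true ORRs of 35% or below is not harm either, since the protocol takes 35% as the historical control.

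Nor do the documents establish the large risks at n = 17 to 20. An interim response in Section 10.9 is any PR or CR, with no confirmation asked for in that sentence, and the earliest scan comes at about week 8. Later-dosed participants who have been scanned once can therefore already count as responders. A participant entered on a local MET result joins the EAS only after central confirmation. The extra enrolment in Section 10.10 makes up for participants who fail central confirmation and are outside the EAS, so by itself it implies only a modest overshoot.

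The step at n = 11 also depends on the final N. At N = 31, PP(1, 11) is 0.0103 and the boundary stays at 0. Finally, the protocol's Section 4 and the SAP were not available for this check and may say more about the stages. Even so, they would have to override sentences that Section 10.9 states outright.

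**Conclusion.** The point holds as an internal contradiction with a specific consequence. Section 10.9 fixes the rule on the first 10 evaluable participants and also on everyone in the EAS at the cut-off. Because the EAS has no follow-up condition, the second wording can stop the group partly on people who could not yet have responded. Table 10-7 is correct at n = 10 but does not describe the recalculated rule.

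If only 10 participants are mature, the stop risk at a true ORR of 45% / 50% is 2.3% / 1.1% with 1 to 4 unassessed participants in the EAS and 10.0% / 5.5% with 5 or 6, against 0.25% / 0.10% printed. It would be larger with more. These figures assume a final N of 30, no response yet among the added participants, and an overrun that the protocol does not let one estimate because it gives no accrual rate. If all counted participants are mature, the risk at ORR 45% stays below 2% up to n = 21. The problem is therefore the immature participants and not the recalculation itself. The change should be made, but this is not evidence that the design is unsound.

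**What to change.** In Section 10.9, limit both the responder count and the denominator at the Group 5 interim to EAS participants who have met the trigger: two on-treatment assessments, radiological progression, or discontinuation. Then choose one of two forms:

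1. Use the first 10 such participants and keep the boundary at 0.
2. Use all such participants, recalculate the boundary on their number, and print the boundary and the stop probabilities by true ORR for each plausible n.

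Reword the sentences on the first 10 and on all evaluable participants so that they describe the same set. Later-dosed participants can be listed descriptively.

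The cost is a wording change and, for the second form, a short table. No extra participants are needed. The small downside is that early responses from later-dosed participants do not enter the formal look.

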## 10.10 Sample size calculation

### Phase Ib part

Cohorts of 3 to 6 evaluable participants will be enrolled in the dose-escalation part including at least six participants at the MTD/RP2D level, as described in [Section 6.2.3](#). Multiple cohorts may be sequentially enrolled to the same dose level. Additional cohorts of 1 to 6 participants may be enrolled at any dose level below the estimated MTD/RP2D for further elaboration of safety and pharmacokinetic parameters as required. At least 18 participants are expected to be treated in the dose escalation part, for the model to have reasonable operating characteristics relating to its MTD recommendation.

### Phase II part

Approximately 145 participants (40 in Group 1, 5 in Group 2, 40 in Group 3, 30 in Group 4 and 30 in Group 5) will be enrolled in the study if Group 3 or Group 5 is not stopped for futility at the time of the interim analysis.

#### Group 1 (EGFRmut, any T790M, any MET, 2/4L antineoplastic, EGFR TKI resistant)

As specified in [Section 4.1](#), the number of participants harboring the T790M mutation among sub-groups 1a and 1c is minimum 20, for participants who do not harbor the T790M mutation among sub-groups 1b and 1d it is also minimum 20. The actual total sample size in Group 1 may be greater than 40.

[Table 10-4](#) shows the 95% credible intervals based on the posterior distribution for different observed number of responses. The highlighted rows show examples that might be observed for the T790M+ or T790M- participants. If 5 responses out of 20 participants are observed, there is 95% probability that the ORR is between 9.1% and 44.3%, whereas it is between 32.0% and 73.1% when 11 responses are observed. To have at least 97.5% probability that the ORR is larger than 50%, 15 or more responses are required.

**Table 10-4 Credible intervals for assumed observed responses in Group 1**

Sample Size	Observed responses	Median	95% Credible Interval
20	4	0.188	[0.062, 0.386]
20	5	0.236	[0.091, 0.443]
20	6	0.285	[0.124, 0.497]
20	10	0.480	[0.277, 0.688]
20	11	0.529	[0.320, 0.731]
20	12	0.577	[0.365, 0.772]
20	15	0.724	[0.512, 0.882]

#### Group 2 (EGFRmut, de novo T790M, any MET, 1/3L antineoplastic, EGFR TKI naïve)

The sample size for this group is based on the potential number of participants with the rare condition who can be enrolled into the study and not on formal sample size or operating characteristic calculations.

### Group 3 (EGFRmut, T790M negative, any MET, 1L antineoplastic)

The operating characteristics of the statistical design are presented below with the probabilities to stop for futility at the interim analysis and to declare preliminary anti-tumor activity of the study treatment at the primary analysis (observing at least 22 responses in 40 participants) under different true ORR values (see also [Table 10-5](#)).

The actual total sample size in Group 3 may be greater than 40.

- If the true ORR is 40%, it is likely to stop at the interim analysis (probability 0.596) and the probability to declare preliminary anti-tumor activity at the end of the study is low (0.038).
- If the true ORR is 55%, the probability to stop at the interim analysis is low, 0.131, and the probability to declare preliminary anti-tumor activity at the end of the study is 0.553.
- If the true ORR is 70%, it is highly unlikely that the study would be stopped at the interim analysis (probability 0.005) and the probability to declare preliminary anti-tumor activity at the end of the study is very high (0.982).

**Table 10-5 Operating characteristics for ORR in Group 3**

True ORR	Probability to stop for futility at IA	Success probability at primary analysis
0.40	0.596	0.038
0.45	0.414	0.129
0.50	0.252	0.309
0.55	0.131	0.553
0.60	0.057	0.780
0.65	0.020	0.923
0.70	0.005	0.982
0.75	0.001	0.998
0.80	0.000	1.000

### Group 4 (EGFRmut, any T790M, any MET, 1L (treatment naïve) 2-3L antineoplastic)

The size of this group is based on practical considerations, not on formal sample size or operating characteristic calculations. The precision of estimates in the PK analysis which can be expected with the planned sample size of 20 participants with full PK blood samples is detailed below.

Based on published data ([Tan et al 2017](#)) at the RP2D (capmatinib 400 mg b.i.d. + 100 mg q.d. nazartinib) based on the Phase Ib data, the CV% of Cmax and AUC0-12 for v would be at most 49.4% and 48.3%, and the CV% of Cmax and AUC0-24 for nazartinib would be at most 58.9% and 78.7%. To be conservative, the CV% of 49.4% for capmatinib PK and 78.7% for nazartinib PK was used in the calculation below.

When combining fasted PK data from Phase Ib (n=10) at the RP2D and fasted PK from Group 1 (approximately n=3) and from Group 3 (n=10) in Phase II, a total of about n=23 participants would have full PK in the fasted state. In Group 4 in Phase II, n=20 participants may have full PK in the fed state.

With such sample size (n=23 in the fasted status, and n=20 in the fed status), the half-width of a 90% CI on the log-scale is 0.239 and 0.355 from the observed mean difference of log (PK) for capmatinib and nazartinib, respectively. Once transformed back to the original scale, this

translates into the 90% CI shown in [Table 10-6](#), under different assumptions of what the true ratio of the PK parameters is.

**Table 10-6 Expected 90% confidence limits for different ratios of geometric means**

True ratio	Capmatinib PK		nazartinib PK	
	Lower Limit of 90% CI	Upper Limit of 90% CI	Lower Limit of 90% CI	Upper Limit of 90% CI
0.70	0.550	0.890	0.490	1.001
0.80	0.629	1.107	0.560	1.143
1.00	0.786	1.272	0.700	1.429
1.25	0.983	1.590	0.875	1.787
1.50	1.179	1.908	1.049	2.144
2.00	1.573	2.544	1.399	2.859
2.50	1.966	3.179	1.749	3.573

**Group 5 (EGFRmut, T790M-, MET GCN  $\geq$  5, 2L, EGFR TKI resistant)**

The operating characteristics (with 30 participants and assuming an interim analysis after Stage 1 at 10 participants) were determined for the primary objective to estimate the treatment effect of capmatinib monotherapy. Based on available data ([Soria et al 2015](#), [Moket al 2017](#)), the ORR in the historical control for this population is expected to be around 35%. The success criterion defined in [Section 10.5.2](#) requires an estimated ORR of  $>45\%$  and a lower bound of the two-sided 95% exact CI of  $>35\%$  to conclude that the antitumor activity is of clinical interest.

[Table 10-7](#) presents the probability of stopping at the interim analysis, the probability for a positive conclusion (i.e., not stopped at IA for futility and success criteria met at final analysis after stage 2) and for a negative conclusion (i.e., not stopped at IA for futility but success criteria not met at final analysis) under different underlying true ORR of capmatinib monotherapy.

The operating characteristics have up to around 35% probability of stopping the trial for futility when the true ORR is  $\leq 35\%$ . Also, when the true ORR is 45% then the probability of positive conclusion at the final analysis with 30 participants is ca. 50%. If the true ORR is 50% or higher, the probability of a positive conclusion at the final analysis with 30 participants is  $>70\%$ .

To adjust for potential discordance between local vs central MET amplification testing results, additional participants may be enrolled to ensure there are at least 10 in stage 1 and 30 in total MET amplified participants centrally confirmed by Novartis-designated laboratory.

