### 10.6.2 Statistical model, hypothesis, and method of analysis

The analysis of the primary endpoint will be performed for participants in the EAS who were treated with capmatinib monotherapy and based on the time period of monotherapy treatment. ORR is defined as the proportion of participants with confirmed best overall response of CR or PR, and will be assessed by the investigator according to RECIST 1.1.

The analysis of Group 5 data will be performed when all participants enrolled in the group have completed at least 6 treatment cycles (about 6 months) or discontinued prior to that time for any reason, provided the Group 5 continued into Stage 2.

The primary efficacy endpoint ORR will be estimated and the 2-sided exact 95% CI (Clopper and Pearson 1934) provided. Capmatinib monotherapy treatment will be considered to have clinically relevant efficacy if the following criteria are fulfilled:

- the ORR estimate is > 45% and
- the lower bound of the two-sided 95% exact CI is >35%.

Based on historical data (Soria et al 2015, Mok et al 2017), the ORR in this population is expected to be around 35% and the threshold of 45% is considered of clinical interest.

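### Group 5: Table 10-7 leaves out the confidence-interval condition, so the stated chance of success above 70% at a true ORR of 50% is 29% under the written rule

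*Protocol*

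**What the plan says.** Section 10.6.2 sets two joint conditions for declaring that capmatinib monotherapy has clinically relevant efficacy in Group 5. The first is "the ORR estimate is > 45% and" the second "the lower bound of the two-sided 95% exact CI is >35"%. The interval method is fixed in the same section: "The primary efficacy endpoint ORR will be estimated and the 2-sided exact 95% CI (Clopper and Pearson 1934) provided".

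Section 10.10 (Group 5) repeats both conditions. It defines a positive conclusion as not having stopped for futility and having met the success criteria after stage 2. The design basis is "The operating characteristics (with 30 participants and assuming an interim analysis after Stage 1 at 10 participants"), and Section 10.9 stops the group "if 0 response out of the first evaluable 10 participants is observed".

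In Table 10-7 the column headed "Probability of positive conclusion at final analysis" gives 12.63% at a true ORR of 0.35, 28.55% at 0.40, 49.75% at 0.45, 70.76% at 0.50 and 86.44% at 0.55. The text summarises this as roughly 50% at a true ORR of 45%, and adds: "If the true ORR is 50% or higher, the probability of a positive conclusion at the final analysis with 30 participants" exceeds 70%.

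**The concern.** With 30 participants an exact 95% interval is wide. At 14 of 30 the estimate is 46.7% and the lower bound 28.3%, a gap of more than 18 percentage points. An estimate just above 45% therefore cannot have a lower bound above 35%, and the interval condition should be much the stricter of the two. Yet Table 10-7 shows close to a 50% chance of success at a true ORR of 45%, which is what one expects if only the point estimate is tested against 45%.

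These operating characteristics are the only quantitative support given for the size of Group 5. If they belong to a different rule, the sponsor, ethics committees and investigators have been given a much too favourable picture of the design. A result of 14, 15 or 16 responders would pass the rule behind the table and fail the rule in Section 10.6.2, which invites argument after the data are seen. A failure to meet the criterion could also be read as lack of activity when the design had little chance of success at the response rate the protocol calls clinically interesting.

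**Working it through.** **Inputs, all from the protocol.** N = 30 with an interim at 10 (Section 10.10); stop at 0 of 10 (Section 10.9); success if the estimate is above 45% and the Clopper-Pearson two-sided 95% lower bound is above 35% (Section 10.6.2); true ORR values as in Table 10-7.

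**Formula.** Let r be the smallest number of responders out of 30 that counts as success. Then

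P(positive) = Σ over k = 1 to 10 of P[Bin(10, p) = k] × P[Bin(20, p) ≥ r − k],

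which equals P[Bin(30, p) ≥ r] − (1 − p)^10 × P[Bin(20, p) ≥ r].

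**Step 1: reproduce the stated figure.** The point-estimate condition alone gives r = 14, since 13/30 = 43.3% and 14/30 = 46.7%. At p = 0.50: 0.70767 − 0.00098 × 0.05766 = 0.7076, the stated 70.76%. With r = 14, all nine rows of the table reproduce to two decimals in both the positive and the negative column.

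**Step 2: find the threshold under the full rule.** The exact lower bound at x of 30 is the 2.5% quantile of Beta(x, 31 − x).

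| Responders | Estimate | Exact 95% lower bound | Estimate > 45% | Bound > 35% |
|---|---|---|---|---|
| 14 | 46.7% | 28.3% | yes | no |
| 15 | 50.0% | 31.3% | yes | no |
| 16 | 53.3% | 34.3% | yes | no |
| 17 | 56.7% | 37.4% | yes | yes |

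So r = 17. At this sample size the 45% condition never decides the outcome.

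**Step 3: recompute with r = 17.** At p = 0.50: 0.292332 − 0.000977 × 0.00129 = 0.29233, i.e. 29.23%. All values in per cent:

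| True ORR | Stop at interim | Positive, stated | Positive, written rule | Negative, stated | Negative, written rule |
|---|---|---|---|---|---|
| 0.10 | 34.87 | 0.00 | 0.00 | 65.13 | 65.13 |
| 0.20 | 10.74 | 0.09 | 0.00 | 89.17 | 89.26 |
| 0.25 | 5.63 | 0.82 | 0.02 | 93.55 | 94.35 |
| 0.30 | 2.82 | 4.00 | 0.21 | 93.17 | 96.96 |
| 0.35 | 1.35 | 12.63 | 1.24 | 86.02 | 97.42 |
| 0.40 | 0.60 | 28.55 | 4.81 | 70.85 | 94.58 |
| 0.45 | 0.25 | 49.75 | 13.56 | 50.00 | 86.19 |
| 0.50 | 0.10 | 70.76 | 29.23 | 29.14 | 70.67 |
| 0.55 | 0.03 | 86.44 | 50.25 | 13.53 | 49.72 |

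At a true ORR of 0.60, which the table does not cover, the written rule gives 71.45%. The stopping column is correct as printed. The stated negative entry of 29.14% at 0.50 lies close to the corrected positive entry of 29.23% only because the binomial is symmetric at p = 0.5.

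The difference between the two positive columns is the chance of landing on 14 to 16 responders, where the two rules disagree: 70.76 − 29.23 = 41.53% at a true ORR of 0.50.

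**Step 4: could another reading rescue the figure?** At p = 0.50, 95% Wald, Wilson, Agresti-Coull and Jeffreys intervals each give r = 16 and 42.8%. An exact 90% interval also gives r = 16 and 42.8%; an exact 80% interval gives r = 15 and 57.2%. None reaches 70.76%. Keeping the written rule and the interim but enlarging the evaluable set gives 43.4% at N = 36, 43.7% at N = 40, 55.6% at N = 50, 65.0% at N = 60 and 72.5% at N = 70.

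**The case against.** The best defence is that the decision rule is sound. Section 10.6.2 is unambiguous and can be applied as written at the final analysis; only a planning table and two sentences are wrong. The stated aim is to estimate the ORR, and the estimate and exact interval will be reported, so a reader need not rely on pass or fail alone. That stands, and it is why misreading a negative result is a risk and not a certainty.

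Three narrower points also stand:

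- The protocol never calls 12.63% a false-positive rate. It is simply the tabulated probability at a true ORR of 0.35.
- The count of 17 holds only for exactly 30 evaluable participants. The protocol plans approximately 30, with extras allowed to reach 30 centrally confirmed.
- The interim definition of a responder does not ask for confirmation, while the final endpoint does. The calculation treats the two alike. Any effect is negligible at the ORR values that matter, since stopping has a probability of only 0.10% at 0.50.

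None of this reconciles the table with the rule. Both stand in the same protocol, so no detail left to the SAP can make one follow from the other.

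**Conclusion.** The concern holds. Table 10-7 and the accompanying text describe a rule of at least 14 responders in 30, while Sections 10.6.2 and 10.10 require what amounts to at least 17 in 30. Under the written rule the chance of a positive conclusion is 29.23% at a true ORR of 50%, 41.53 percentage points below the stated figure. It is 13.56% at 45% and 50.25% at 55%, and it passes 70% only at about 60%. At the historical 35% it is 1.24%, about a tenth of the stated 12.63%.

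This rests on N = 30 evaluable participants, the 0-of-10 stop and the Clopper-Pearson 95% interval, all fixed by the protocol, and on Section 10.6.2 being the intended rule. If it is not, the rule is wrong instead of the table. Either way the document must be corrected.

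**What to change.** Keep the two-part rule in Section 10.6.2 as the operative one and add, as an illustration, that with 30 evaluable participants it requires at least 17 responders. Replace the positive and negative columns of Table 10-7 with the written-rule columns above, and add a row for a true ORR of 0.60 (71.45% positive). Replace the two sentences in Section 10.10 with: about 14% at a true ORR of 45%, 29% at 50%, 50% at 55% and 71% at 60%. In the same paragraph, the reference to Section 10.5.2 for the success criterion should point to Section 10.6.2.

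If 14 of 30 was what the sponsor meant, the interval condition must be removed and a 12.63% chance of a positive conclusion at the historical rate accepted openly. If the sponsor wants both the written rule and more than 70% at a true ORR of 50%, the confidence level or the sample size has to change; with the interval and interim rule unchanged, that takes about 70 evaluable participants.

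Correcting the figures alone means one table and one paragraph, with no extra participants, provided the sponsor accepts the less favourable characteristics.
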